It is unsurprising that lifestyle modification would improve symptoms of VM. There is sufficient evidence in the literature that lifestyle modification is beneficial for non-VM forms of migraine that we will refer to collectively as migraine. Migraine symptoms have been shown to improve in 63-93% of patients through dietary interventions and in 48.9% of patients through cognitive behavioral therapy to treat insomnia. Conversely, missing meals or fasting has been reported to trigger migraines in as many as 57% of migraineurs. Finally, low-level physical activity and exercise has been shown to reduce migraine symptoms. However, avoidance of dietary triggers, restful sleep, mealtime regularity, and exercise have not yet been systematically investigated as a comprehensive approach to management of symptoms of VM.

More work is needed to prospectively determine the outcomes of lifestyle modification on VM. As noted, VM accounts for a large percentage of individuals affected by symptoms of dizziness and imbalance. It is also important to understand the effects of lifestyle modification on VM to assist with evaluation of other interventions, including pharmacological ones. The purpose of the current investigation was to prospectively evaluate the effects of common lifestyle modifications on symptoms of dizziness and headache in patients diagnosed with definite VM.

Materials and Methods

Design and Participants

Participants were recruited from patients seen for consultation for dizziness and/or imbalance in the John S. Odess Otolaryngology and Head and Neck Surgery Clinic. Consultations were provided by two nurse practitioners and one otolaryngologist. All clinicians were experienced in diagnosis and management of dizziness and imbalance including VM. All adult patients diagnosed with definite VM using the consensus criteria were eligible for inclusion. Patients who were determined to need pharmacological management at initial consultation were excluded.

Forty-one patients were consented and enrolled as participants. Thirteen (31.7%) of the participants did not complete this investigation for the following reasons: seven requested pharmacological intervention during the experimental period and were withdrawn, one was diagnosed with Rocky Mountain Spotted Fever and withdrawn, and five were lost to follow-up. Twenty-eight participants (68.3%) completed the investigation. Analysis was performed for the 28 participants with completed data sets. Mean age was 46.4 years (standard deviation = 16) and participants were 78.6% female.

Study Materials

Participants completed the Dizziness Handicap Inventory (DHI), Headache Disability Inventory (HDI), and lifestyle scale (Table 1) prior to and again after lifestyle modification intervention. The DHI and HDI are 25-item self-report tools that examine impact of dizziness symptoms and headache symptoms on HRQOL. Lower total scores indicate less impact of the symptoms on HRQOL. The lifestyle scale was developed for this study to gain an understanding of self-perceived restful sleep, mealtime regularity, exercise, and avoidance of dietary triggers. Participants indicated their level of agreement with each statement using a 5-point Likert scale. Higher scores indicated better self-perceived compliance with the lifestyle component.

Procedures

Data were collected either paper/pencil or using an online Redcap survey, depending on participant preference and in-person COVID-related limitations. Participants completed the DHI, HDI, and lifestyle scale during a clinic appointment before and after the intervention. On average, participants completed post-intervention surveys after 105 days (standard deviation = 78.1).

Intervention

The intervention addressed four areas related to lifestyle modification that have been shown to be effective in at least some patients with VM or with migraine. These areas were restful sleep, mealtime regularity, exercise, and elimination of dietary triggers. The diagnosing clinicians provided a four-page handout (see supplemental digital content) with information about each area after their diagnosis and after the patient completed the informed consent process.

For restful sleep, we provided helpful tips adapted from the National Institute on Aging. To bring focus to mealtime regularity, the handout provided informational statements that skipping or missing meals can lead to symptoms and the participant should prepare ahead to ensure they are eating on a schedule. We also encouraged participants to continue or resume a preferred exercise program or start some type of formal exercise. A sample walking program from the National Heart, Lung, and Blood Institute²⁵ was adapted and provided along with the caveat to only begin such a program if medically cleared. Finally, we combined information from published research¹⁶ and other publicly available resources to develop a comprehensive elimination list of potential dietary triggers. Participants were asked to follow this four-part intervention until follow-up, with an initial goal of at least 60 days.

Statistical Methods

Scores on the lifestyle scale were analyzed using linear mixed-effects models with two within-participant factors, Intervention (pre-intervention, post-intervention) and Lifestyle Factor (restful sleep, exercise, mealtime regularity, avoiding dietary triggers).

Scores on the two handicap inventories, DHI and HDI, were also analyzed using linear mixed-effects models with two within-participant factors, Intervention (pre-intervention, post-intervention) and Inventory (DHI, HDI). For all models, participant was included as a random factor. Models were constructed using the *lmer* function of the *lme* package in R and were analyzed using the *anova* function in base R. Significant main effects and interactions were evaluated using the *emmeans* function of the *emmeans* package. Pairwise comparisons were adjusted to account for false-discovery rates.

Inter-individual variability in pre- to post-intervention scores were analyzed by calculating change scores (subtracting post-intervention from pre-intervention scores [DHI and HDI] or subtracting pre-intervention from post-intervention scores [lifestyle scale]). Two linear mixed models were constructed, one for each inventory, with the change scores as the dependent variable. Independent variables were participant sex, age, and lifestyle change score for each lifestyle question. Models were constructed and analyzed with the *lmer* and *anova* functions, respectively.

Finally, to determine individual participant post-intervention change, we compared pre- and post-total scores for the DHI and HDI. On the DHI, a change of 18 points is considered significant. For the HDI, a change of 29 points is considered significant.

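### The single-arm pre-post contrast cannot separate an effect of lifestyle modification from other causes of change, so the purpose and the result should be worded as change after the handout

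*Combined protocol and SAP*

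**What the plan says.** All references are to the combined protocol and SAP.

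- **Purpose** (last paragraph before Materials and Methods): to "prospectively evaluate the effects of common lifestyle modifications on symptoms of dizziness and headache".
- **Entry** (Design and Participants): "Participants were recruited from patients seen for consultation for dizziness and/or imbalance".
- **Exposure** (Intervention): "The diagnosing clinicians provided a four-page handout" once diagnosis and consent were complete. No comparison group, run-in or repeated baseline is described.
- **Measurement** (Procedures): "Participants completed the DHI, HDI, and lifestyle scale during a clinic appointment before and after the intervention".
- **Symptom test** (Statistical Methods): a linear mixed model with "two within-participant factors, Intervention (pre-intervention, post-intervention) and Inventory (DHI, HDI").
- **Change-score models** (Statistical Methods): "Two linear mixed models were constructed, one for each inventory, with the change scores as the dependent variable". Each of these models has six predictors, namely sex, age and the change on each of the four lifestyle items. Their declared use is different: "Inter-individual variability in pre- to post-intervention scores were analyzed by calculating change scores". They are examined with anova, which tests model terms. No predicted change at zero lifestyle change is named.

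Statistical Methods also sets individual thresholds of 18 points (DHI) and 29 points (HDI). The text does not mention natural course, regression to the mean or non-specific response.

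**The concern.** The purpose is causal and the factor that tests it is labelled Intervention, but what the factor measures is the passage from one occasion to another. People who seek a consultation tend to do so when symptoms are bad, so some fall in DHI and HDI is to be expected whatever they then do. Being diagnosed and advised may also shift self-reported scores. If a fall from these sources is labelled an effect of lifestyle modification, the study claims something its design cannot show. This matters beyond the study, because the introduction wants the lifestyle results to help in judging other treatments, including drugs.

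**Working it through.** **1. Inputs.** From the documents: 28 analysed participants; one group measured twice; change-score models with sex, age and four lifestyle change scores; a DHI threshold of 18 points. The documents give no SD of change, no expected fall and no power calculation, so there is no design figure to reproduce. All SDs, falls and lifestyle-change distributions below are assumptions.

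**2. What the pre/post term estimates.** Expected mean change = lifestyle effect + natural course + regression to the mean + response to being seen. The design gives one estimate of the sum and no second equation to split it.

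**3. How easily the sum is significant with no lifestyle effect.** Two-sided 5% paired t test, n = 28, 27 df, critical value 2.052, noncentrality = fall / SD × √28.

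| Assumed fall | Assumed SD | Noncentrality | Chance of significance |
|---|---|---|---|
| 5 | 20 | 1.32 | 25% |
| 5 | 15 | 1.76 | 40% |
| 8 | 20 | 2.12 | 53% |
| 8 | 15 | 2.82 | 78% |

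Both falls are below the 18-point DHI threshold. This is a one-inventory simplification of the planned joint DHI/HDI model.

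**4. Two opposite explanations, same test result.** Simulation with n = 28, residual SD 18, a mean lifestyle change of 1 per item (SD 1, inter-item correlation 0.3) and a mean fall of 10 points. The fitted model contained the four lifestyle changes only.

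- None of the fall due to lifestyle: pre-post test significant in 82% of runs; mean intercept (predicted change at zero lifestyle change) 9.9.
- All of it due to lifestyle (2.5 points per item unit × 4 items × 1 = 10): significant in 75%; mean intercept 0.1.

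The pre-post test does not distinguish the cases. The intercept does on average, but with item reliability of 0.7 or 0.5 the second intercept drifts up to 1.8 or 3.5. Reverse causation was not simulated.

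**5. Precision of the zero-change prediction.** The model has an intercept and 6 slopes, so residual df = 28 − 7 = 21 and the critical value is 2.080. With residual SD 15 to 20, mean item change 0.5 to 1 (SD 1), item correlations 0.2 to 0.4, and age and sex centred, the average standard error is 3.8 to 8.1 points.

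- 95% half-width: 2.080 × 3.8 = 7.9, up to 2.080 × 8.1 = 16.8.
- For comparison, the raw mean change: 2.052 × 15/√28 = 5.8, up to 2.052 × 20/√28 = 7.8.
- Chance that the interval excludes zero when the true non-lifestyle fall is 5 points: 24% (SE 3.8) down to 9% (SE 8.1). For 8 points: 52% down to 16%.

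Over a wider grid (SD 12 to 24, mean item change 0.5 to 1.5, item correlation 0 or 0.3) the half-width runs from 6.3 to 32.6 points.

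**6. Model form.** Statistical Methods puts participant as a random factor in all models. The change-score models have one row per participant: 28 rows and 28 levels. The random effect is not separable from the residual, so ordinary regression is the form that can be fitted. Uncentred, the intercept would refer to age 0.

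**The case against.** **The documents contain no interpretation rule.** Only background and methods are available. A reader might infer that the plan will report any significant pre-post fall as a lifestyle effect. No sentence says so, and individual change is also judged against the 18- and 29-point thresholds. This stands. The point rests on the causal purpose and the factor label, not on a conclusion the study has drawn.

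**The internal comparison is weak.** A reader might infer that the change-score models already hold the answer, namely how much participants improve with no lifestyle change. They do not. The interval would usually include zero even if real drift were present (step 5), and that could be misread as no natural improvement. Zero change is also not the same as no lifestyle modification: someone already at the top of a 5-point item, or continuing an existing exercise programme, scores zero while complying. This stands, and it reduces the estimate to an optional sensitivity analysis.

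**The slopes are no better as causal evidence.** A reader might want to rest the effect claim on the association between lifestyle change and symptom change, which is already planned. Lifestyle change is self-perceived, not randomised, and recorded on the same occasions as DHI and HDI. A participant whose dizziness eases for another reason may sleep and exercise better. Resting the claim there exchanges one confounded contrast for another. This stands.

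None of these objections makes the pre-post contrast able to isolate a lifestyle effect.

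**Conclusion.** The point holds as a limit on what the study can claim. The pre-post term measures change after the handout from all causes together, and the wording of the purpose goes further than that. A non-lifestyle fall of 5 to 8 points would be significant in 25% to 78% of studies of this size, assuming a change SD of 15 to 20 and a simple paired test. The exact percentages depend on those assumptions; the inability to separate causes does not.

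The documents do not support the stronger view that the planned models can supply the missing control. The zero-change estimate is imprecise, mixes non-adopters with people who already complied, is pushed upward by measurement error when lifestyle change does help, and does not correct for the analysis being restricted to completers. Seven of the 13 non-completers were withdrawn after requesting drug treatment.

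**What to change.** 1. Restate the purpose, and describe the pre-post term as *change in DHI and HDI after receiving the lifestyle handout*, not as an effect of lifestyle modification. State that natural course, regression to the mean and response to being seen cannot be excluded.
2. Optionally, as a labelled sensitivity estimate, fit the two change-score models as ordinary regressions (one row per participant) with age and sex centred. Report the predicted change at zero lifestyle change with its 95% CI beside the raw mean change. Say that it is imprecise, that an interval including zero does not show absence of natural improvement, and that zero change includes participants who already complied.
3. Report the lifestyle-change slopes as associations only, open to reverse causation and self-report error, and base no causal claim on them.

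Cost: some rewording and a few lines of analysis, with no new data. The downside is a weaker headline claim and, if item 2 is adopted, one more imprecise estimate to report.

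### Seven of 41 participants were withdrawn when they requested a drug and are missing from the 28 analysed, so the completer-only DHI and HDI results may overstate the benefit

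*Combined protocol and SAP*

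**What the plan says.** Under Materials and Methods, Design and Participants, 41 patients were enrolled and 13 did not complete. Of the 13, "seven requested pharmacological intervention during the experimental period and were withdrawn"; of the other six, "one was diagnosed with Rocky Mountain Spotted Fever and withdrawn, and five were lost to follow-up". The analysis set is then fixed: "Analysis was performed for the 28 participants with completed data sets".

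The same section sets the entry rule: "Patients who were determined to need pharmacological management at initial consultation were excluded". The seven requests therefore arose after enrolment.

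Procedures describes two assessment points: "Participants completed the DHI, HDI, and lifestyle scale during a clinic appointment before and after the intervention". No assessment at withdrawal is mentioned, and the text does not say whether exit scores exist.

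Statistical Methods gives two analyses that bear on benefit. The first is the group comparison: "Scores on the two handicap inventories, DHI and HDI, were also analyzed using linear mixed-effects models with two within-participant factors", namely pre/post and inventory. The second is individual change: "we compared pre- and post-total scores for the DHI and HDI". For that, "On the DHI, a change of 18 points is considered significant", and the HDI threshold is 29 points.

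**The concern.** The study sets out to evaluate what lifestyle modification does for dizziness and headache in definite vestibular migraine. A participant who asks for a drug part-way through is plausibly someone for whom lifestyle modification alone was not enough. If so, the reason for leaving is tied to the outcome, and analysing only those who stayed selects for better results.

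The text describes only pre-post comparisons and no control group, so the DHI and HDI findings rest on change in whoever remains. Both the mean change and the proportion passing the 18-point or 29-point threshold could look better than they were among the people who started.

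The mixed model does not remove the problem. Such a model can use incomplete records, but the plan limits it to complete data sets. Even with their baselines added, the seven would have no described post-score, and the estimate would rest on a missing-at-random assumption that symptom-driven requests may break. The individual-change analysis needs both scores, so non-completers drop out of its denominator.

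**Working it through.** **Inputs (Design and Participants):** 41 enrolled; 7 withdrawn at a drug request; 1 withdrawn for another diagnosis; 5 lost to follow-up; 28 analysed.

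**Reproducing the stated flow:** 7 + 1 + 5 = 13; 41 − 13 = 28; 13/41 = 31.7%; 28/41 = 68.3%. All match the document.

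**Share affected:** 7/41 = 17.1% (95% Wilson interval 8.5% to 31.3%). The seven are 7/13 = 53.8% of the non-completers.

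**Mean change.** Let D be the mean improvement in the 28 and f the ratio of the non-completers' mean improvement to D. Neither is given, so both are assumptions.

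- Seven added: (28D + 7fD)/35
- All 13 added: (28D + 13fD)/41

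| f | Mean over 35 | Mean over 41 | If D = 18 DHI points: over 35 | If D = 18 DHI points: over 41 |
|---|---|---|---|---|
| 0 (no change) | 0.80 D | 0.68 D | 14.4 | 12.3 |
| 0.5 | 0.90 D | 0.84 D | 16.2 | 15.1 |
| 1 (same as completers) | 1.00 D | 1.00 D | 18.0 | 18.0 |

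D = 18 borrows the individual threshold purely as a round illustration. No change is not a floor, because some may have worsened: at f = −0.5 the mean over 35 is (28 − 3.5)/35 = 0.70 D. If the seven did not change and the other six behaved like completers, the mean over 41 is 34/41 = 0.83 D.

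**Individual change.** Let r be the number of completers who pass a threshold (not given). With the seven counted as non-responders, the completer proportion is multiplied by 28/35 = 0.80; with all 13, by 28/41 = 0.68.

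| r (assumed) | r/28 | r/35 | r/41 |
|---|---|---|---|
| 7 | 25% | 20% | 17.1% |
| 14 | 50% | 40% | 34.1% |
| 21 | 75% | 60% | 51.2% |

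**The case against.** **Withdrawal was proper.** Stopping study follow-up when a drug is started keeps post-scores free of drug effects and fits the entry exclusion. Change among people who stay on lifestyle modification without drugs is also a legitimate target. This is accepted. But withdrawing someone does not require losing their last score on lifestyle modification alone, and the stated purpose is not limited to those content to continue. The text also does not say whether withdrawal came before the first dose, so any exit score would need checking on that point.

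**The attrition is disclosed.** The counts, the reasons and the analysis set are all stated, and a reader given r could form r/35 and r/41. That is true, but baselines of non-completers cannot be reconstructed that way. The available text ends with the statistical methods, so a caveat or comparison could appear in a results or limitations section that is not included here.

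**Direction and size are not shown.** The requests come without scores, timing or reasons; an early request could reflect preference or severity. This stands, and it is why the finding says only that the results may overstate the benefit. The sign of the mean change is also fairly robust: to bring it to zero over 35, the seven would have to worsen by 4D on average (28D/7), and over 41 all 13 would have to worsen by about 2.15D (28D/13). What is in doubt is how large the benefit is.

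**The 41-person scenario reaches too far.** It counts as a non-responder one person withdrawn for an infection plausibly unrelated to response. That is fair, so r/41 serves only as an outer bound; r/35 is the figure that addresses the drug requests.

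**Conclusion.** The concern holds. As written, the DHI/HDI model and the individual-change results describe the 28 completers, and they leave out seven of 41 people whose exit is plausibly linked to the outcome.

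The direction of bias is inferred and its size cannot be computed from the documents. For the seven alone, assuming they fared between no change and the same change as completers, the mean lies between 0.80 and 1.00 of the completer mean. It would be lower if they worsened. Counting them as non-responders cuts the response proportion by one fifth. These are scenarios under assumed values and do not estimate what happened. The issue should be addressed: the correction is cheap, and shifts of this size could change how a reader judges the benefit. Confidence is medium.

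**What to change.** **Current data**

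1. Use any exit scores that exist for the seven.
2. If there are none, report the 18-point and 29-point results as r/35 (the seven as non-responders) and r/41 (all 13 as non-responders) beside r/28, labelled as conservative bounds.
3. Where pre-scores exist, compare baseline DHI and HDI of the seven, and of all 13, with those of the 28.
4. State beside the DHI/HDI model that it describes completers only, and give the no-change scenarios (0.80 and 0.68 of its mean change), labelled as scenarios.

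The cost is two extra denominators, one descriptive comparison and one or two sentences. With 7 or 13 non-completers, the comparison can describe a baseline difference but cannot rule one out.

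**Continuation or successor study**

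5. When a participant requests a drug, give the existing DHI, HDI and lifestyle scale before the first dose, record the day, and use these as the last scores on lifestyle modification alone. Care does not change.

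This needs one sentence in Procedures and one extra use of existing questionnaires for about one participant in six. The drawback is that exit scores come early, possibly before the 60-day goal, and are timed by symptoms, so they may lean toward worse values. Some participants will not respond.

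### Every analysis uses only the 28 completers of 41 enrolled, and the methods text describes no all-enrolled or sensitivity analysis; bias towards benefit is plausible but not shown

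*Combined protocol and SAP*

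**What the plan says.** Design and Participants gives the flow: "Forty-one patients were consented and enrolled as participants". Thirteen did not complete. Of these, "seven requested pharmacological intervention during the experimental period and were withdrawn", one was withdrawn for another diagnosis and five were lost to follow-up. The analysis set follows: "Analysis was performed for the 28 participants with completed data sets".

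The purpose, at the end of the introduction, is "to prospectively evaluate the effects of common lifestyle modifications on symptoms of dizziness and headache in patients diagnosed with definite VM".

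Study Materials says that the Dizziness Handicap Inventory (DHI), the Headache Disability Inventory (HDI) and the lifestyle scale were completed "prior to and again after lifestyle modification intervention".

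Statistical Methods describes four things:
- a mixed model for the lifestyle scale;
- a mixed model for DHI and HDI, with Intervention and Inventory as within-participant factors;
- predictor models of change ("Two linear mixed models were constructed, one for each inventory, with the change scores as the dependent variable");
- an individual comparison ("to determine individual participant post-intervention change, we compared pre- and post-total scores for the DHI and HDI") against 18 points on the DHI and 29 on the HDI.

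It mentions no handling of missing data, no all-enrolled analysis, no sensitivity analysis and no comparison of completers with non-completers.

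**The concern.** The largest single group left out is defined by something that happened during the intervention. In a study of a non-drug approach, asking for drugs may mean that the approach was not giving enough relief. If so, the 28 are a selected group, and the mean DHI and HDI change, the individual-change results, the lifestyle-scale results and the predictor models all describe people who stayed without drug treatment and completed follow-up, rather than everyone given the handout.

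The introduction also says that knowing the effect of lifestyle change should help in evaluating other treatments, drugs included. A reference result that leaves out those who asked for drugs can mislead in that use unless it is labelled. From the methods text, a reader cannot tell whether the conclusion would survive including the other 13.

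**Working it through.** **Flow (Design and Participants).** 7 + 1 + 5 = 13; 41 − 13 = 28; 13/41 = 31.7%; 28/41 = 68.3%. The stated figures reproduce. The seven are 7/41 = 17.1% of those enrolled and 7/13 = 53.8% of the non-completers.

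The documents give no outcome for the 13 and no results for the 28, so everything below is a formula with assumed inputs.

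**Individual change.** Let k of the 28 meet the improvement threshold. Count the seven as not improved and take the other six both ways. The result over 41 runs from k/41 to (k + 6)/41.

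| k (assumed) | k/28 | k/41 | (k + 6)/41 |
|---|---|---|---|
| 7 | 25% | 17.1% | 31.7% |
| 14 | 50% | 34.1% | 48.8% |
| 21 | 75% | 51.2% | 65.9% |

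If the seven might also have improved, the upper end is (k + 13)/41: 48.8%, 65.9% and 82.9%. Each completer figure lies inside that wider range, so the counts alone do not fix a direction.

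**Mean change.** Statistical Methods defines DHI and HDI change as pre minus post, so positive is improvement. Let M be the completers' mean change and g the amount by which non-completers fall short of it.
- Only the seven differ: mean over 41 = [34M + 7(M − g)]/41 = M − 7g/41.
- All 13 differ: mean over 41 = [28M + 13(M − g)]/41 = M − 13g/41.

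| g (assumed, points) | Completer mean minus all-enrolled mean, seven differ | Same, all 13 differ |
|---|---|---|
| −10 | −1.71 | −3.17 |
| 0 | 0 | 0 |
| 5 | 0.85 | 1.59 |
| 10 | 1.71 | 3.17 |
| 20 | 3.41 | 6.34 |

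A negative gap means that the completer result understates benefit. If those who differ had no change at all (g = M), the mean over 41 is 34/41 = 0.829 of M, or 28/41 = 0.683 of M.

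**When the interval reaches zero.** Let L be the lower 95% limit of the completers' mean change. With g held fixed and the completer standard error kept, the lower limit over 41 is L − 7g/41 or L − 13g/41. It reaches zero at:
- g = 41L/7 = 5.86L if only the seven differ (L = 1, 2, 4 gives 5.86, 11.71, 23.43 points);
- g = 41L/13 = 3.15L if all 13 differ (3.15, 6.31, 12.62 points).

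This treats the gap as known; allowing for uncertainty about the 13 would lower these values.

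**Why the convention must be stated.** Suppose instead that the seven are given a fixed mean change d, with the other six matching completers. The estimate is (34M + 7d)/41, its standard error shrinks by 34/41, and the lower limit is (34L + 7d)/41, which is zero at d = −34L/7. At d = 0 the estimate and its standard error shrink together, so significance cannot change.

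Example, assuming SD of change 20 and M = 10: SE = 20/√28 = 3.78 and L = 10 − 2.052 × 3.78 = 2.24 (t quantile, 27 df).
- Fixed gap: g = 41 × 2.24/7 = 13.12, so d = 10 − 13.12 = −3.12.
- Fixed d: d = −34 × 2.24/7 = −10.88. At d = −3.12 the lower limit would be (34 × 2.24 − 7 × 3.12)/41 = +1.32, not zero.

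The two conventions give different answers and must not be mixed.

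**The case against.** The losses are set out in full, with reasons, immediately before the analysis set is named, so nothing is concealed. The restriction also has a rationale. Patients judged to need drugs at the first consultation were excluded, and scores taken after starting drugs would mix two effects. Counting the seven as not improved is only one way to handle them. The text is a methods section, so baseline comparisons or stated limitations may exist elsewhere.

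Most of this stands. It limits the point to the methods text, makes outcome without drugs a legitimate question, and means that any figure for the seven is an assumption. It does not answer the point: disclosing counts does not show whether the conclusion depends on them, and bounds and labelling need no scores taken on drugs.

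Two stronger readings are tempting.
- A reader might infer that the completer result overstates benefit. The documents give no reasons behind the drug requests, no timing and no scores for the seven, so this is not shown and the opposite is possible.
- A reader might take "participants were 78.6% female" as a misdescription of the enrolled sample. It directly follows the sentence naming the 28, and 22/28 = 78.6%, so it is what one would expect and shows no error.

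**Conclusion.** The point holds as a gap in analysis and labelling, and it should be fixed. It is certain from the text that the analyses rest on 28 of 41, and that Statistical Methods describes no all-enrolled or sensitivity analysis. That the omission favours benefit is plausible, because more than half of the non-completers left for a reason that may be tied to outcome; it remains an inference.

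The size cannot be computed from the documents. Under the stated assumptions a 50% response could read as 34.1% to 48.8% over 41, and a 10-point gap would move the mean by 1.71 points (seven differ) or 3.17 points (all 13 differ). These are scenarios, not estimates of bias. The lack of a control arm is a separate limit and plays no part here.

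**What to change.** Add to Statistical Methods:

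1. As a sensitivity analysis, report the 18-point DHI and 29-point HDI individual-change results over all 41, with the seven counted as not improved and the other six shown both ways: k/41 to (k + 6)/41.
2. Where baseline forms of the 13 are held, fit the DHI/HDI and lifestyle mixed models to all available data. State that this corrects only for loss explained by observed scores; the drug requests arose after baseline, so baseline scores may not explain them. Compare age, sex and baseline scores of the 28 and the 13.
3. For mean DHI and HDI change, give a range over 41 for stated gaps g on both sides of zero, with the tipping gaps 41L/7 (only the seven differ) and 41L/13 (all 13 differ). State that g is held fixed and the completer standard error is used, and do not combine this with a fixed value for the non-completers' change.
4. Keep the completer results and the change-score predictor models, which need post-intervention scores. Label them as applying to those who stayed without drug treatment and completed follow-up.

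The cost is a little re-analysis and about a paragraph of text. Items 1, 3 and 4 use only completer results and known counts. Item 2 depends on baseline forms that the documents do not confirm are held for the 13. The headline may become less favourable, and item 1 over-corrects if some of the seven had improved. Only analysis and reporting change.
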